Appendix G. Study Drug Packaging and Administration

Prior to Amendment 4

During the Double-Blind Induction Period

Week	Standard Induction Dose	High Induction Dose
0 (Baseline)	Blinded study drug adalimumab 2.4 mg/kg Maximum dose of 160 mg Maximum amount to administer is 3.2 mL	Blinded study drug adalimumab 2.4 mg/kg Maximum dose of 160 mg Maximum amount to administer is 3.2 mL
1	Matching PBO Maximum amount to administer is 3.2 mL	Blinded study drug adalimumab 2.4 mg/kg Maximum dose of 160 mg Maximum amount to administer is 3.2 mL
2	Blinded study drug adalimumab 1.2 mg/kg Maximum dose of 80 mg Maximum amount to administer is 1.6 mL	Blinded study drug adalimumab 1.2 mg/kg Maximum dose of 80 mg Maximum amount to administer is 1.6 mL
4	Blinded study drug adalimumab 0.6 mg/kg Maximum dose of 40 mg Maximum amount to administer is 0.8 mL	Blinded study drug adalimumab 0.6 mg/kg Maximum dose of 40 mg Maximum amount to administer is 0.8 mL
6	Blinded study drug adalimumab 0.6 mg/kg Maximum dose of 40 mg Maximum amount to administer is 0.8 mL	Blinded study drug adalimumab 0.6 mg/kg Maximum dose of 40 mg Maximum amount to administer is 0.8 mL

During the Maintenance Period

Week	PBO	Standard Maintenance Dose	High Maintenance Dose
8 – 50 i.e., Wks 8, 10, 12, 14, 16, 18 to Wk 50)	Matching PBO Maximum amount to administer is 0.8 mL	Blinded Study Drug adalimumab 0.6 mg/kg Maximum dose of 40 mg Maximum amount to administer is 0.8 mL	Blinded Study Drug adalimumab 0.6 mg/kg Maximum dose of 40 mg Maximum amount to administer is 0.8 mL
9 – 51 i.e., Wks 9, 11, 13, 15, 17, 19 ... to Wk 51	Matching PBO Maximum amount to administer is 0.8 mL	Matching PBO Maximum amount to administer is 0.8 mL	Blinded Study Drug adalimumab 0.6 mg/kg Maximum dose of 40 mg Maximum amount to administer is 0.8 mL

Disease Flare During Maintenance Period

Week	PBO		Standard Maintenance Dose		High Maintenance Dose	
	Re-Induction Dose of 2.4 mg/kg (max 160 mg)	Dose 0.6 mg/kg (max 40 mg)	Re-Induction Dose of 2.4 mg/kg (max 160 mg)	Dose 0.6 mg/kg (max 40 mg)	Re-Induction Dose of 2.4 mg/kg (max 160 mg)	Dose 0.6 mg/kg (max 40 mg)
Disease Flare						
Re-Induction Dose (1 st time) At or after Week 12	Blinded study drug adalimumab 2.4 mg/kg Maximum dose of 160 mg	Blinded study drug adalimumab 0.6 mg/kg Maximum dose of 40 mg Plus Matching Placebo Maximum amount to administer is 3.2 mL	Blinded study drug adalimumab 2.4 mg/kg Maximum dose of 160 mg	Blinded study drug adalimumab 0.6 mg/kg Maximum dose of 40 mg Plus Matching Placebo Maximum amount to administer is 3.2 mL	Blinded study drug adalimumab 2.4 mg/kg Maximum dose of 160 mg	Blinded study drug adalimumab 0.6 mg/kg Maximum dose of 40 mg Plus Matching Placebo Maximum amount to administer is 3.2 mL

Disease Flare During Maintenance Period (Continued)

Week	PBO		Standard Maintenance Dose		High Maintenance Dose	
	Re-Induction Dose of 2.4 mg/kg (max 160 mg)	Dose 0.6 mg/kg (max 40 mg)	Re-Induction Dose of 2.4 mg/kg (max 160 mg)	Dose 0.6 mg/kg (max 40 mg)	Re-Induction Dose of 2.4 mg/kg (max 160 mg)	Dose 0.6 mg/kg (max 40 mg)
One week after Re-Induction dose	If subject receives Re-Induction dose at site on Even week (i.e., Wk 22, 24, 26, ...), then subject must start with vial 2 at home at the week after Re-Induction dose.		If subject receives Re-Induction dose at site on Even week (i.e., Wk 22, 24, 26, ...), then subject must start with vial 2 at home at the week after Re-Induction dose.		If subject receives Re-Induction dose at site on Even week (i.e., Wk 22, 24, 26, ...), then subject must start with vial 2 at home at the week after Re-Induction dose.	
	Matching PBO Maximum amount to administer is 0.8 mL		Matching PBO Maximum amount to administer is 0.8 mL		Blinded study drug adalimumab 0.6 mg/kg Maximum dose of 40 mg Maximum amount to administer is 0.8 mL	
	The following weeks, subject will use vial 1, then vial 2, continue like this until next site visit.		The following weeks, subject will use vial 1, then vial 2, continue like this until next site visit.		The following weeks, subject will use vial 1, then vial 2, continue like this until next site visit.	

Disease Flare During Maintenance Period (Continued)

Week	PBO		Standard Maintenance Dose		High Maintenance Dose	
	Re-Induction Dose of 2.4 mg/kg (max 160 mg)	Dose 0.6 mg/kg (max 40 mg)	Re-Induction Dose of 2.4 mg/kg (max 160 mg)	Dose 0.6 mg/kg (max 40 mg)	Re-Induction Dose of 2.4 mg/kg (max 160 mg)	Dose 0.6 mg/kg (max 40 mg)
One week after Re-Induction dose (continued)	If subject receives Re-Induction dose at site on Odd week (i.e., Wk 21, 23, 25, ...), then subject must start with vial 1 at home at the week after Re-Induction dose.	If subject receives Re-Induction dose at site on Odd week (i.e., Wk 21, 23, 25, ...), then subject must start with vial 1 at home at the week after Re-Induction dose.	If subject receives Re-Induction dose at site on Odd week (i.e., Wk 21, 23, 25, ...), then subject must start with vial 1 at home at the week after Re-Induction dose.	If subject receives Re-Induction dose at site on Odd week (i.e., Wk 21, 23, 25, ...), then subject must start with vial 1 at home at the week after Re-Induction dose.	If subject receives Re-Induction dose at site on Odd week (i.e., Wk 21, 23, 25, ...), then subject must start with vial 1 at home at the week after Re-Induction dose.	If subject receives Re-Induction dose at site on Odd week (i.e., Wk 21, 23, 25, ...), then subject must start with vial 1 at home at the week after Re-Induction dose.
	Blinded study drug adalimumab 0.6 mg/kg Maximum dose of 40 mg Maximum amount to administer is 0.8 mL The following weeks, subject will use vial 2, then vial 1, continue like this until next site visit.	Blinded study drug adalimumab 0.6 mg/kg Maximum dose of 40 mg Maximum amount to administer is 0.8 mL The following weeks, subject will use vial 2, then vial 1, continue like this until next site visit.	Blinded study drug adalimumab 0.6 mg/kg Maximum dose of 40 mg Maximum amount to administer is 0.8 mL The following weeks, subject will use vial 2, then vial 1, continue like this until next site visit.	Blinded study drug adalimumab 0.6 mg/kg Maximum dose of 40 mg Maximum amount to administer is 0.8 mL The following weeks, subject will use vial 2, then vial 1, continue like this until next site visit.	Blinded study drug adalimumab 0.6 mg/kg Maximum dose of 40 mg Maximum amount to administer is 0.8 mL The following weeks, subject will use vial 2, then vial 1, continue like this until next site visit.	Blinded study drug adalimumab 0.6 mg/kg Maximum dose of 40 mg Maximum amount to administer is 0.8 mL The following weeks, subject will use vial 2, then vial 1, continue like this until next site visit.

Disease Flare During Maintenance Period (Continued)

Escape to Open-Label Drug (Weight Based)

Disease Flare adalimumab 0.6 mg/kg
2nd Time (at least Maximum dose of 40 mg
 after 4 weeks of *Maximum amount to administer is 0.8 mL*
 re-induction dose) Administered every week

Dose Escalation (MAX DOSE – NOT Weight Based)

Disease Flare Adalimumab 40 mg/0.8 mL
3rd Time (after at Adalimumab 40 mg
 least 4 weeks on *Amount to administer is 0.8 mL*
 open-label standard Administered every week
 dose)

Dose De-Escalation and Dose Re-Escalation During Maintenance Period

Dose De-Escalation	Open-label study drug adalimumab 40 mg/0.8 mL Administered every other week
Dose Re-Escalation	Open-label study drug adalimumab 40 mg/0.8 mL Administered every week

After Amendment 4

During the Open-Label Induction Period

Week	High Induction Dose
0 (Baseline)	Open-label study drug adalimumab 2.4 mg/kg Maximum dose of 160 mg Maximum amount to administer is 3.2 mL
1	Open-label study drug adalimumab 2.4 mg/kg Maximum dose of 160 mg Maximum amount to administer is 3.2 mL
2	Open-label study drug adalimumab 1.2 mg/kg Maximum dose of 80 mg Maximum amount to administer is 1.6 mL
4	Open-label study drug adalimumab 0.6 mg/kg Maximum dose of 40 mg Maximum amount to administer is 0.8 mL
6	Open-label study drug adalimumab 0.6 mg/kg Maximum dose of 40 mg Maximum amount to administer is 0.8 mL

During the Maintenance Period

Week	Standard Maintenance Dose	High Maintenance Dose
8 – 50 i.e., Wks 8, 10, 12, 14, 16, 18 to Wk 50)	Blinded Study Drug adalimumab 0.6 mg/kg Maximum dose of 40 mg Maximum amount to administer is 0.8 mL	Blinded Study Drug adalimumab 0.6 mg/kg Maximum dose of 40 mg Maximum amount to administer is 0.8 mL
9 – 51 i.e., Wks 9, 11, 13, 15, 17, 19... to Wk 51	Matching PBO Maximum amount to administer is 0.8 mL	Blinded Study Drug adalimumab 0.6 mg/kg Maximum dose of 40 mg Maximum amount to administer is 0.8 mL

Disease Flare During Maintenance Period

Week	Standard Maintenance Dose		High Maintenance Dose	
	Re-Induction Dose of 2.4 mg/kg (max 160 mg)	Dose 0.6 mg/kg (max 40 mg)	Re-Induction Dose of 2.4 mg/kg (max 160 mg)	Dose 0.6 mg/kg (max 40 mg)
Disease Flare				
Re-Induction Dose (1 st time) At or after Week 12	Blinded study drug adalimumab 2.4 mg/kg Maximum dose of 160 mg Maximum amount to administer is 3.2 mL	Blinded study drug adalimumab 0.6 mg/kg Maximum dose of 40 mg Plus Matching Placebo Maximum amount to administer is 3.2 mL	Blinded study drug adalimumab 2.4 mg/kg Maximum dose of 160 mg Maximum amount to administer is 3.2 mL	Blinded study drug adalimumab 0.6 mg/kg Maximum dose of 40 mg Plus Matching Placebo Maximum amount to administer is 3.2 mL
One week after Re-Induction dose	If subject receives Re-Induction dose at site on Even week (i.e., Wk 22, 24, 26, ...), then subject must start with vial 2 at home at the week after Re-Induction dose. Matching PBO Maximum amount to administer is 0.8 mL The following weeks, subject will use vial 1, then vial 2, continue like this until next site visit.		If subject receives Re-Induction dose at site on Even week (i.e., Wk 22, 24, 26, ...), then subject must start with vial 2 at home at the week after Re-Induction dose. Blinded study drug adalimumab 0.6 mg/kg Maximum dose of 40 mg Maximum amount to administer is 0.8 mL The following weeks, subject will use vial 1, then vial 2, continue like this until next site visit.	

Disease Flare During Maintenance Period (Continued)

Week	Standard Maintenance Dose		High Maintenance Dose	
	Re-Induction Dose of 2.4 mg/kg (max 160 mg)	Dose 0.6 mg/kg (max 40 mg)	Re-Induction Dose of 2.4 mg/kg (max 160 mg)	Dose 0.6 mg/kg (max 40 mg)
Disease Flare				
One week after Re-Induction dose (continued)	
If subject receives Re-Induction dose at site on Odd week (i.e., Wk 21, 23, 25, ...), then subject must start with vial 1 at home at the week after Re-Induction dose.
 
Blinded study drug adalimumab 0.6 mg/kg Maximum dose of 40 mg Maximum amount to administer is 0.8 mL
 
The following weeks, subject will use vial 2, then vial 1, continue like this until next site visit.
		
If subject receives Re-Induction dose at site on Odd week (i.e., Wk 21, 23, 25, ...), then subject must start with vial 1 at home at the week after Re-Induction dose.
 
Blinded study drug adalimumab 0.6 mg/kg Maximum dose of 40 mg Maximum amount to administer is 0.8 mL
 
The following weeks, subject will use vial 2, then vial 1, continue like this until next site visit.
	

Escape to Open-Label Drug (Weight Based)

Disease Flare 2nd Time (at least after 4 weeks of re-induction dose)	adalimumab 0.6 mg/kg Maximum dose of 40 mg Maximum amount to administer is 0.8 mL Administered every week
--	---

Dose Escalation (MAX DOSE – NOT Weight Based)

Disease Flare 3rd Time (after at least 4 weeks on open-label standard dose)	Adalimumab 40 mg/0.8 mL Adalimumab 40 mg Amount to administer is 0.8 mL Administered every week
---	---

Dose De-Escalation and Dose Re-Escalation During Maintenance Period

Dose De-Escalation	Open-label study drug adalimumab 40 mg/0.8 mL Administered every other week
Dose Re-Escalation	Open-label study drug adalimumab 40 mg/0.8 mL Administered every week

Appendix H. Body Weight Adjusted Volumes of Study Drug for Administration of Induction and Maintenance Doses

Part 1. Body Weight Adjusted Volumes of Study Drug for Administration of Induction Dose at BL and Week 1

Weight (Kg)	Administered (# of vial used)	Kit 1		Kit 2		Administered (# of vial used)	Weight (Kg)	Kit 1		Kit 2		Administered (# of vial used)	Weight (Kg)	Kit 1		Kit 2	
		Vial 1	Vial 2	Vial 1	Vial 2			Vial 1	Vial 2	Vial 1	Vial 2			Vial 1	Vial 2		
14	1 x	0.67	NA	NA	NA	4 x	36	0.43	0.43	0.43	0.43	4 x	58	0.70	0.70	0.70	0.70
15	1 x	0.72	NA	NA	NA	4 x	37	0.44	0.44	0.44	0.44	4 x	59	0.71	0.71	0.71	0.71
16	1 x	0.77	NA	NA	NA	4 x	38	0.46	0.46	0.46	0.46	4 x	60	0.72	0.72	0.72	0.72
17	2 x	0.41	0.41	NA	NA	4 x	39	0.47	0.47	0.47	0.47	4 x	61	0.73	0.73	0.73	0.73
18	2 x	0.43	0.43	NA	NA	4 x	40	0.48	0.48	0.48	0.48	4 x	62	0.74	0.74	0.74	0.74
19	2 x	0.46	0.46	NA	NA	4 x	41	0.49	0.49	0.49	0.49	4 x	63	0.76	0.76	0.76	0.76
20	2 x	0.48	0.48	NA	NA	4 x	42	0.50	0.50	0.50	0.50	4 x	64	0.77	0.77	0.77	0.77
21	2 x	0.50	0.50	NA	NA	4 x	43	0.52	0.52	0.52	0.52	4 x	65	0.78	0.78	0.78	0.78
22	2 x	0.53	0.53	NA	NA	4 x	44	0.53	0.53	0.53	0.53	4 x	66	0.79	0.79	0.79	0.79
23	2 x	0.55	0.55	NA	NA	4 x	45	0.54	0.54	0.54	0.54	4 x	67	0.80	0.80	0.80	0.80
24	2 x	0.58	0.58	NA	NA	4 x	46	0.55	0.55	0.55	0.55	4 x	68	0.80	0.80	0.80	0.80
25	2 x	0.60	0.60	NA	NA	4 x	47	0.56	0.56	0.56	0.56	4 x	69	0.80	0.80	0.80	0.80
26	2 x	0.62	0.62	NA	NA	4 x	48	0.58	0.58	0.58	0.58	4 x	70	0.80	0.80	0.80	0.80
27	2 x	0.65	0.65	NA	NA	4 x	49	0.59	0.59	0.59	0.59	4 x	71	0.80	0.80	0.80	0.80
28	2 x	0.67	0.67	NA	NA	4 x	50	0.60	0.60	0.60	0.60	4 x	72	0.80	0.80	0.80	0.80
29	2 x	0.70	0.70	NA	NA	4 x	51	0.61	0.61	0.61	0.61	4 x	73	0.80	0.80	0.80	0.80
30	2 x	0.72	0.72	NA	NA	4 x	52	0.62	0.62	0.62	0.62	4 x	74	0.80	0.80	0.80	0.80
31	2 x	0.74	0.74	NA	NA	4 x	53	0.64	0.64	0.64	0.64	4 x	75	0.80	0.80	0.80	0.80

Weight (Kg)	Administered (# of vial used)		Kit 1 Vial 1		Kit 2 Vial 1		Weight (Kg)		Administered (# of vial used)		Kit 1 Vial 1		Kit 2 Vial 1		Weight (Kg)		Administered (# of vial used)		Kit 1 Vial 1		Kit 2 Vial 1	
	Kit 1 Vial 1	Kit 2 Vial 1	Kit 1 Vial 2	Kit 2 Vial 2	Kit 1 Vial 1	Kit 2 Vial 1	Kit 1 Vial 2	Kit 2 Vial 2	Kit 1 Vial 1	Kit 2 Vial 1	Kit 1 Vial 2	Kit 2 Vial 2	Kit 1 Vial 1	Kit 2 Vial 1	Kit 1 Vial 2	Kit 2 Vial 2	Kit 1 Vial 1	Kit 2 Vial 1	Kit 1 Vial 2	Kit 2 Vial 1	Kit 1 Vial 2	Kit 2 Vial 2
32	0.77	NA	0.77	NA	0.65	NA	54	4 x	0.65	0.65	0.65	0.65	0.80	0.80	76	4 x	0.80	0.80	0.80	0.80	0.80	0.80
33	0.79	NA	0.79	NA	0.66	NA	55	4 x	0.66	0.66	0.66	0.66	0.80	0.80	77	4 x	0.80	0.80	0.80	0.80	0.80	0.80
34	0.41	0.41	0.41	0.41	0.67	0.41	56	4 x	0.67	0.67	0.67	0.67	0.80	0.80	78	4 x	0.80	0.80	0.80	0.80	0.80	0.80
35	0.42	0.42	0.42	0.42	0.68	0.42	57	4 x	0.68	0.68	0.68	0.68	0.80	0.80	79	4 x	0.80	0.80	0.80	0.80	0.80	0.80
															80	4 x	0.80	0.80	0.80	0.80	0.80	0.80

Part 2. Body Weight Adjusted Volumes of Study Drug for Administration of Induction Dose at Week 2

Weight (Kg)	Administered (# of vial used)		Kit 1 Vial 1		Kit 1 Vial 2		Weight (Kg)		Administered (# of vial used)		Kit 1 Vial 1		Kit 1 Vial 2	
	Administered (# of vial used)	Kit 1 Vial 1	Kit 1 Vial 2	Kit 1 Vial 1	Kit 1 Vial 2	Weight (Kg)	Administered (# of vial used)	Kit 1 Vial 1	Kit 1 Vial 2	Weight (Kg)	Administered (# of vial used)	Kit 1 Vial 1	Kit 1 Vial 2	
14	1 x	0.34	NA	0.44	0.44	37	2 x	0.44	0.44	60	2 x	0.72	0.72	
15	1 x	0.36	NA	0.46	0.46	38	2 x	0.46	0.46	61	2 x	0.73	0.73	
16	1 x	0.38	NA	0.47	0.47	39	2 x	0.47	0.47	62	2 x	0.74	0.74	
17	1 x	0.41	NA	0.48	0.48	40	2 x	0.48	0.48	63	2 x	0.76	0.76	
18	1 x	0.43	NA	0.49	0.49	41	2 x	0.49	0.49	64	2 x	0.77	0.77	
19	1 x	0.46	NA	0.50	0.50	42	2 x	0.50	0.50	65	2 x	0.78	0.78	
20	1 x	0.48	NA	0.52	0.52	43	2 x	0.52	0.52	66	2 x	0.79	0.79	
21	1 x	0.50	NA	0.53	0.53	44	2 x	0.53	0.53	67	2 x	0.80	0.80	
22	1 x	0.53	NA	0.54	0.54	45	2 x	0.54	0.54	68	2 x	0.80	0.80	
23	1 x	0.55	NA	0.55	0.55	46	2 x	0.55	0.55	69	2 x	0.80	0.80	
24	1 x	0.58	NA	0.56	0.56	47	2 x	0.56	0.56	70	2 x	0.80	0.80	
25	1 x	0.60	NA	0.58	0.58	48	2 x	0.58	0.58	71	2 x	0.80	0.80	

Weight (Kg)	Administered (# of vial used)	Kit 1 Vial 1	Kit 1 Vial 2	Weight (Kg)	Administered (# of vial used)	Kit 1 Vial 1	Kit 1 Vial 2	Weight (Kg)	Administered (# of vial used)	Kit 1 Vial 1	Kit 1 Vial 2	Weight (Kg)	Administered (# of vial used)	Kit 1 Vial 1	Kit 1 Vial 2
26	1 x	0.62	NA	49	2 x	0.59	0.59	72	2 x	0.80	0.80	72	2 x	0.80	0.80
27	1 x	0.65	NA	50	2 x	0.60	0.60	73	2 x	0.80	0.80	73	2 x	0.80	0.80
28	1 x	0.67	NA	51	2 x	0.61	0.61	74	2 x	0.80	0.80	74	2 x	0.80	0.80
29	1 x	0.70	NA	52	2 x	0.62	0.62	75	2 x	0.80	0.80	75	2 x	0.80	0.80
30	1 x	0.72	NA	53	2 x	0.64	0.64	76	2 x	0.80	0.80	76	2 x	0.80	0.80
31	1 x	0.74	NA	54	2 x	0.65	0.65	77	2 x	0.80	0.80	77	2 x	0.80	0.80
32	1 x	0.77	NA	55	2 x	0.66	0.66	78	2 x	0.80	0.80	78	2 x	0.80	0.80
33	1 x	0.79	NA	56	2 x	0.67	0.67	79	2 x	0.80	0.80	79	2 x	0.80	0.80
34	2 x	0.41	0.41	57	2 x	0.68	0.68	80	2 x	0.80	0.80	80	2 x	0.80	0.80
35	2 x	0.42	0.42	58	2 x	0.70	0.70								
36	2 x	0.43	0.43	59	2 x	0.71	0.71								

Part 3. Body Weight Adjusted Volumes of Study Drug for Administration of Induction Dose at Week 4 and 6

Weight (Kg)	Administered (# of vial used)	Week 4 Kit 1 Vial 1 Volume (ml)	Week 6 Kit 1 Vial 2 Volume (ml)	Weight (Kg)	Administered (# of vial used)	Week 4 Kit 1 Vial 1 Volume (ml)	Week 6 Kit 1 Vial 2 Volume (ml)	Weight (Kg)	Administered (# of vial used)	Week 4 Kit 1 Vial 1 Volume (ml)	Week 6 Kit 1 Vial 2 Volume (ml)
14	1 x	0.17	0.17	36	1 x	0.43	0.43	58	1 x	0.70	0.70
15	1 x	0.18	0.18	37	1 x	0.44	0.44	59	1 x	0.71	0.71
16	1 x	0.19	0.19	38	1 x	0.46	0.46	60	1 x	0.72	0.72
17	1 x	0.20	0.20	39	1 x	0.47	0.47	61	1 x	0.73	0.73

Adalimumab
M11-290 Protocol Amendment 5
EudraCT 2013-003032-77

Weight (Kg)	Administered (# of vial used)	Week 4 Kit 1 Vial 1 Volume (ml)	Week 6 Kit 1 Vial 2 Volume (ml)	Weight (Kg)	Administered (# of vial used)	Week 4 Kit 1 Vial 1 Volume (ml)	Week 6 Kit 1 Vial 2 Volume (ml)	Weight (Kg)	Administered (# of vial used)	Week 4 Kit 1 Vial 1 Volume (ml)	Week 6 Kit 1 Vial 2 Volume (ml)	Weight (Kg)	Administered (# of vial used)	Week 4 Kit 1 Vial 1 Volume (ml)	Week 6 Kit 1 Vial 2 Volume (ml)
18	1 x	0.22	0.22	40	1 x	0.48	0.48	62	1 x	0.74	0.74	62	1 x	0.74	0.74
19	1 x	0.23	0.23	41	1 x	0.49	0.49	63	1 x	0.76	0.76	63	1 x	0.76	0.76
20	1 x	0.24	0.24	42	1 x	0.50	0.50	64	1 x	0.77	0.77	64	1 x	0.77	0.77
21	1 x	0.25	0.25	43	1 x	0.52	0.52	65	1 x	0.78	0.78	65	1 x	0.78	0.78
22	1 x	0.26	0.26	44	1 x	0.53	0.53	66	1 x	0.79	0.79	66	1 x	0.79	0.79
23	1 x	0.28	0.28	45	1 x	0.54	0.54	67	1 x	0.80	0.80	67	1 x	0.80	0.80
24	1 x	0.29	0.29	46	1 x	0.55	0.55	68	1 x	0.80	0.80	68	1 x	0.80	0.80
25	1 x	0.30	0.30	47	1 x	0.56	0.56	69	1 x	0.80	0.80	69	1 x	0.80	0.80
26	1 x	0.31	0.31	48	1 x	0.58	0.58	70	1 x	0.80	0.80	70	1 x	0.80	0.80
27	1 x	0.32	0.32	49	1 x	0.59	0.59	71	1 x	0.80	0.80	71	1 x	0.80	0.80
28	1 x	0.34	0.34	50	1 x	0.60	0.60	72	1 x	0.80	0.80	72	1 x	0.80	0.80
29	1 x	0.35	0.35	51	1 x	0.61	0.61	73	1 x	0.80	0.80	73	1 x	0.80	0.80
30	1 x	0.36	0.36	52	1 x	0.62	0.62	74	1 x	0.80	0.80	74	1 x	0.80	0.80
31	1 x	0.37	0.37	53	1 x	0.64	0.64	75	1 x	0.80	0.80	75	1 x	0.80	0.80
32	1 x	0.38	0.38	54	1 x	0.65	0.65	76	1 x	0.80	0.80	76	1 x	0.80	0.80
33	1 x	0.40	0.40	55	1 x	0.66	0.66	77	1 x	0.80	0.80	77	1 x	0.80	0.80
34	1 x	0.41	0.41	56	1 x	0.67	0.67	78	1 x	0.80	0.80	78	1 x	0.80	0.80
35	1 x	0.42	0.42	57	1 x	0.68	0.68	79	1 x	0.80	0.80	79	1 x	0.80	0.80
				80	1 x			80	1 x			80	1 x		

Part 4. Body Weight Adjusted Volumes of Study Drug for Administration of Maintenance Dose Starting at Week 8 to Week 51

Weight (Kg)	Administered (# of vial used)	Volume (ml)	Weight (Kg)	Administered (# of vial used)	Volume (ml)	Weight (Kg)	Administered (# of vial used)	Volume (ml)	Weight (Kg)	Administered (# of vial used)	Volume (ml)
14	1 x	0.17	36	1 x	0.43	58	1 x	0.70			
15	1 x	0.18	37	1 x	0.44	59	1 x	0.71			
16	1 x	0.19	38	1 x	0.46	60	1 x	0.72			
17	1 x	0.20	39	1 x	0.47	61	1 x	0.73			
18	1 x	0.22	40	1 x	0.48	62	1 x	0.74			
19	1 x	0.23	41	1 x	0.49	63	1 x	0.76			
20	1 x	0.24	42	1 x	0.50	64	1 x	0.77			
21	1 x	0.25	43	1 x	0.52	65	1 x	0.78			
22	1 x	0.26	44	1 x	0.53	66	1 x	0.79			
23	1 x	0.28	45	1 x	0.54	67	1 x	0.80			
24	1 x	0.29	46	1 x	0.55	68	1 x	0.80			
25	1 x	0.30	47	1 x	0.56	69	1 x	0.80			
26	1 x	0.31	48	1 x	0.58	70	1 x	0.80			
27	1 x	0.32	49	1 x	0.59	71	1 x	0.80			
28	1 x	0.34	50	1 x	0.60	72	1 x	0.80			
29	1 x	0.35	51	1 x	0.61	73	1 x	0.80			
30	1 x	0.36	52	1 x	0.62	74	1 x	0.80			
31	1 x	0.37	53	1 x	0.64	75	1 x	0.80			

Adalimumab
M11-290 Protocol Amendment 5
EudraCT 2013-003032-77

Weight (Kg)	Administered (# of vial used)	Volume (ml)	Weight (Kg)	Administered (# of vial used)	Volume (ml)	Weight (Kg)	Administered (# of vial used)	Volume (ml)	Weight (Kg)	Administered (# of vial used)	Volume (ml)
32	1 x	0.38	54	1 x	0.65	76	1 x	0.80			
33	1 x	0.40	55	1 x	0.66	77	1 x	0.80			
34	1 x	0.41	56	1 x	0.67	78	1 x	0.80			
35	1 x	0.42	57	1 x	0.68	79	1 x	0.80			
						80	1 x	0.80			

Appendix I. Body Weight Adjusted Volumes of Study Drug for Administration of Dose After Re-Randomization for Disease Flare

Weight (Kg)	Administered (# of vial used)	Kit 1 Vial 1 Volume (ml)	Kit 1 Vial 2 Volume (ml)	Kit 2 Vial 1 Volume (ml)	Kit 2 Vial 2 Volume (ml)
14	4 x	0.17	0.17	0.17	0.17
15	4 x	0.18	0.18	0.18	0.18
16	4 x	0.19	0.19	0.19	0.19
17	4 x	0.20	0.20	0.20	0.20
18	4 x	0.22	0.22	0.22	0.22
19	4 x	0.23	0.23	0.23	0.23
20	4 x	0.24	0.24	0.24	0.24
21	4 x	0.25	0.25	0.25	0.25
22	4 x	0.26	0.26	0.26	0.26
23	4 x	0.28	0.28	0.28	0.28
24	4 x	0.29	0.29	0.29	0.29
25	4 x	0.30	0.30	0.30	0.30
26	4 x	0.31	0.31	0.31	0.31
27	4 x	0.32	0.32	0.32	0.32
28	4 x	0.34	0.34	0.34	0.34
29	4 x	0.35	0.35	0.35	0.35
30	4 x	0.36	0.36	0.36	0.36
31	4 x	0.37	0.37	0.37	0.37
32	4 x	0.38	0.38	0.38	0.38
33	4 x	0.40	0.40	0.40	0.40
34	4 x	0.41	0.41	0.41	0.41
35	4 x	0.42	0.42	0.42	0.42
36	4 x	0.43	0.43	0.43	0.43
37	4 x	0.44	0.44	0.44	0.44
38	4 x	0.46	0.46	0.46	0.46
39	4 x	0.47	0.47	0.47	0.47
40	4 x	0.48	0.48	0.48	0.48
41	4 x	0.49	0.49	0.49	0.49
42	4 x	0.50	0.50	0.50	0.50

Weight (Kg)	Administered (# of vial used)	Kit 1 Vial 1 Volume (ml)	Kit 1 Vial 2 Volume (ml)	Kit 2 Vial 1 Volume (ml)	Kit 2 Vial 2 Volume (ml)
43	4 x	0.52	0.52	0.52	0.52
44	4 x	0.53	0.53	0.53	0.53
45	4 x	0.54	0.54	0.54	0.54
46	4 x	0.55	0.55	0.55	0.55
47	4 x	0.56	0.56	0.56	0.56
48	4 x	0.58	0.58	0.58	0.58
49	4 x	0.59	0.59	0.59	0.59
50	4 x	0.60	0.60	0.60	0.60
51	4 x	0.61	0.61	0.61	0.61
52	4 x	0.62	0.62	0.62	0.62
53	4 x	0.64	0.64	0.64	0.64
54	4 x	0.65	0.65	0.65	0.65
55	4 x	0.66	0.66	0.66	0.66
56	4 x	0.67	0.67	0.67	0.67
57	4 x	0.68	0.68	0.68	0.68
58	4 x	0.70	0.70	0.70	0.70
59	4 x	0.71	0.71	0.71	0.71
60	4 x	0.72	0.72	0.72	0.72
61	4 x	0.73	0.73	0.73	0.73
62	4 x	0.74	0.74	0.74	0.74
63	4 x	0.76	0.76	0.76	0.76
64	4 x	0.77	0.77	0.77	0.77
65	4 x	0.78	0.78	0.78	0.78
66	4 x	0.79	0.79	0.79	0.79
67	4 x	0.80	0.80	0.80	0.80
68	4 x	0.80	0.80	0.80	0.80
69	4 x	0.80	0.80	0.80	0.80
70	4 x	0.80	0.80	0.80	0.80
71	4 x	0.80	0.80	0.80	0.80
72	4 x	0.80	0.80	0.80	0.80
73	4 x	0.80	0.80	0.80	0.80
74	4 x	0.80	0.80	0.80	0.80

Weight (Kg)	Administered (# of vial used)	Kit 1 Vial 1 Volume (ml)	Kit 1 Vial 2 Volume (ml)	Kit 2 Vial 1 Volume (ml)	Kit 2 Vial 2 Volume (ml)
75	4 x	0.80	0.80	0.80	0.80
76	4 x	0.80	0.80	0.80	0.80
77	4 x	0.80	0.80	0.80	0.80
78	4 x	0.80	0.80	0.80	0.80
79	4 x	0.80	0.80	0.80	0.80
80	4 x	0.80	0.80	0.80	0.80

Appendix J. Body Weight Adjusted Volumes of Study Drug for Administration of OL Adalimumab 0.6 mg/kg Dosing (weight based)

Weight (Kg)	Administered (# of vial used)	Volume (ml)	Weight (Kg)	Administered (# of vial used)	Volume (ml)	Weight (Kg)	Administered (# of vial used)	Volume (ml)
14	1 x	0.17	36	1 x	0.43	58	1 x	0.70
15	1 x	0.18	37	1 x	0.44	59	1 x	0.71
16	1 x	0.19	38	1 x	0.46	60	1 x	0.72
17	1 x	0.20	39	1 x	0.47	61	1 x	0.73
18	1 x	0.22	40	1 x	0.48	62	1 x	0.74
19	1 x	0.23	41	1 x	0.49	63	1 x	0.76
20	1 x	0.24	42	1 x	0.50	64	1 x	0.77
21	1 x	0.25	43	1 x	0.52	65	1 x	0.78
22	1 x	0.26	44	1 x	0.53	66	1 x	0.79
23	1 x	0.28	45	1 x	0.54	67	1 x	0.80
24	1 x	0.29	46	1 x	0.55	68	1 x	0.80
25	1 x	0.30	47	1 x	0.56	69	1 x	0.80
26	1 x	0.31	48	1 x	0.58	70	1 x	0.80
27	1 x	0.32	49	1 x	0.59	71	1 x	0.80
28	1 x	0.34	50	1 x	0.60	72	1 x	0.80
29	1 x	0.35	51	1 x	0.61	73	1 x	0.80
30	1 x	0.36	52	1 x	0.62	74	1 x	0.80
31	1 x	0.37	53	1 x	0.64	75	1 x	0.80
32	1 x	0.38	54	1 x	0.65	76	1 x	0.80
33	1 x	0.40	55	1 x	0.66	77	1 x	0.80
34	1 x	0.41	56	1 x	0.67	78	1 x	0.80
35	1 x	0.42	57	1 x	0.68	79	1 x	0.80
						80	1 x	0.80

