Subjects will be expected to remain on blinded therapy throughout the 44-week maintenance period. However, subjects with a disease flare may be re-randomized to receive the following blinded-treatment at or after Week 12, [Figure 4](#).

- Subjects who are randomized to standard maintenance dose (0.6 mg/kg eow [maximum of 40 mg eow]) will be re-randomized to receive either adalimumab re-induction dose (2.4 mg/kg [maximum of 160 mg]) or adalimumab (0.6 mg/kg [maximum of 40 mg]) at the visit. Afterwards, all subjects will resume receiving the standard dose (0.6 mg/kg [maximum of 40 mg] eow) within the original dosing schedule.
- Subjects who are randomized to high maintenance dose (0.6 mg/kg ew [maximum of 40 mg ew]) will be re-randomized to receive either adalimumab re-induction dose (2.4 mg/kg [maximum of 160 mg]) or adalimumab (0.6 mg/kg [maximum of 40 mg]) at the visit. The following week, all subjects will resume receiving the high dose (0.6 mg/kg [maximum of 40 mg] ew).
- Subjects who were randomized to placebo prior to Amendment 4 will be re-randomized to receive either adalimumab re-induction dose (2.4 mg/kg [maximum of 160 mg]) or to receive adalimumab (0.6 mg/kg [maximum of 40 mg]) at the visit. Afterwards, all subjects will receive the standard dose (0.6 mg/kg [maximum of 40 mg] eow) within the original dosing schedule.

If a subject continues to meet the definition of disease flare (2nd time) following at least a 4-week course of blinded therapy since the subject has been re-randomized for the disease flare, they may be switched to open-label adalimumab every week at the dose 0.6 mg/kg [maximum of 40 mg]. *(If a subject was re-randomized at Week 12 (to receive either re-induction dose (2.4 mg/kg [maximum of 160 mg]) or to receive adalimumab (0.6 mg/kg [maximum of 40 mg])), then the earliest that subject could be evaluated to determine if*

they meet the criteria for disease flare for switch to OL (0.6 mg/kg [maximum of 40 mg]) weekly dosing is at Week 16.

If a subject continues to meet the definition of disease flare (3rd time) following a 4-week course of open-label adalimumab every week at the dose 0.6 mg/kg [maximum of 40 mg], they may be switched to receive adalimumab open-label 40 mg ew (maximum dose, not weight based).

Subjects with persistent disease flare while on adalimumab 40 mg ew (max dose) may be withdrawn from the study at the investigator's discretion.

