During open-label rescue therapy, subjects who are responders and have been in remission for at least 8 consecutive weeks ($PMS \leq 2$ with no individual subscore > 1) may have their dosage decreased from ew to eow. The investigator should receive prior approval from the Medical Monitor before taking any action with regard to dose de-escalation.

If subjects demonstrate disease flare after dose de-escalation, subjects also have an opportunity to re-escalate their dose back to adalimumab ew dosing. The investigator should receive prior approval from the Medical Monitor before taking any action with regard to dose re-escalation.

For subjects who meet the criteria for dose change, blood samples (for the determination of adalimumab and AAA concentrations, hs-CRP) will be collected just prior to receiving any dose change (blinded therapy, escape to open-label adalimumab, dose de-escalation and dose re-escalation).

No study drug will be administered or injected at the final visit.

Subjects may discontinue adalimumab treatment at any time during study participation. Subjects who end study participation early will have a Termination Visit. All subjects will have a follow-up phone call approximately 70 days after the last administration of study drug to obtain information on any new or ongoing AEs.

Re-screening

Subjects who initially screen fail for the study may be permitted to re-screen following re-consent. All screening procedures with the possible exceptions noted below will be repeated. The subject must meet all inclusion and none of the exclusion criteria as far as they are assessable at the time of re-screening in order to qualify for the study. There is no minimum period of time a subject must wait to re-screen for the study. If the subject had a complete initial screening evaluation including the assessment of a PPD test, (or equivalent), or Interferon-Gamma Release Assay (IGRA; QuantiFERON-TB Gold In-Tube test or T-SPOT TB test), chest x-ray (if applicable), x-ray of the wrist and ECG, these tests will not be required to be repeated for re-screening provided the conditions noted in Section 5.3.1.1 are met and no more than 3 months (90 days) have passed. An endoscopy will not be required to be repeated for re-screening provided that the prior endoscopy confirmed subject's eligibility, the conditions noted in Section 5.3.1.1 are met and no more than 56 days have passed from Baseline.

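### Appendix G lists open-label de-escalation and re-escalation only as adalimumab 40 mg/0.8 mL, which does not fit the frequency-only change that Section 5.1 allows from weight-based 0.6 mg/kg weekly

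*Protocol*

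**What the plan says.** Protocol Section 5.1 describes open-label rescue in two steps. At a second flare a subject may move to 0.6 mg/kg every week, capped at 40 mg. After a third flare the subject may move to a fixed 40 mg every week, not adjusted for weight.

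De-escalation is then opened to a group defined only by remission on rescue: "During open-label rescue therapy, subjects who are responders and have been in remission for at least 8 consecutive weeks". These subjects "may have their dosage decreased from ew to eow". If they flare again they may "re-escalate their dose back to adalimumab ew dosing". Both changes are described by dosing interval, and neither is tied to one of the two steps. The Synopsis and Section 5.5.1 carry matching text, and SAP Section 4.2 repeats it.

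Appendix G has one row for each change, printed identically in the tables before and after Amendment 4. De-escalation reads "Open-label study drug adalimumab 40 mg/0.8 mL Administered every other week" and re-escalation reads "Open-label study drug adalimumab 40 mg/0.8 mL Administered every week". Neither row gives a mg/kg dose, a maximum or a volume. The second-flare row just above does give a mg/kg dose with a maximum.

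**The concern.** A child on 0.6 mg/kg weekly who qualifies for de-escalation is covered by Section 5.1, but the only Appendix G row for that step shows 40 mg/0.8 mL. A site that takes the row as a dose would give a small child more drug over two weeks than before, at a step the body text calls a decrease. A site that takes it as the vial strength finds no dose in Appendix G for that child.

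The case can arise. Enrolment starts at age 4, the dosing tables start at 14 kg, and SAP Section 10.7 has a subgroup under 40 kg. The weight-based open-label step can begin at Week 16, so eight weeks of remission can be complete by Week 24.

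What is at stake is which dose these children receive, and how to read the concentrations measured afterwards: Protocol Section 8.1.7 summarises trough levels by dose. Section 7.0 also makes an incorrect dose a reportable deviation, which is hard to judge without an unambiguous written dose.

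**Working it through.** **Inputs.** Weight-based step: 0.6 mg/kg weekly, maximum 40 mg (Section 5.1). Product strength: 40 mg in 0.8 mL, that is 40/0.8 = 50 mg/mL (Table 4). De-escalation and re-escalation rows: 40 mg/0.8 mL every other week and every week (Appendix G). Volumes for the weight-based step: Appendix J, 14 to 80 kg.

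**Reproducing the plan's own figures.** Volume = min(0.6 × weight, 40) / 50.
- 14 kg: 8.4/50 = 0.168, printed 0.17 mL
- 20 kg: 12/50 = 0.24, printed 0.24 mL
- 33 kg: 19.8/50 = 0.396, printed 0.40 mL
- 67 kg: 40/50 = 0.80, printed 0.80 mL

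All 32 weights checked (14 to 40, 50, 60, 66, 67 and 80 kg) agree with Appendix J to rounding, so the meaning of the weight-based step is not in doubt.

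**If the Appendix G entry is a dose.** Two-week amount before de-escalation = 2 × min(0.6 × weight, 40) mg; after = 40 mg. They are equal when 1.2 × weight = 40, that is at 33.3 kg. For re-escalation, 40 mg weekly is compared with min(0.6 × weight, 40) mg weekly; they are equal from 40/0.6 = 66.7 kg upwards.

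| Weight (kg) | Weekly dose at 0.6 mg/kg (mg) | Two-week amount before (mg) | 40 mg every other week ÷ before | 40 mg weekly ÷ earlier weekly dose |
|---|---|---|---|---|
| 14 | 8.4 | 16.8 | 2.38 | 4.76 |
| 20 | 12 | 24 | 1.67 | 3.33 |
| 25 | 15 | 30 | 1.33 | 2.67 |
| 30 | 18 | 36 | 1.11 | 2.22 |
| 34 | 20.4 | 40.8 | 0.98 | 1.96 |
| 50 | 30 | 60 | 0.67 | 1.33 |
| 67 | 40 | 80 | 0.50 | 1.00 |

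The last column is also the change in the single injection at de-escalation. Below 66.7 kg, re-escalation to 40 mg weekly would not be a return to the earlier dose.

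**If the entry is only a strength.** The ratios above do not apply. Appendix G then gives product and interval but no dose for a child coming from 0.6 mg/kg. Appendix J does tabulate volumes for that dose, but Section 5.3.1.1 introduces it for the second flare, not for de-escalation.

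**Subjects already on fixed 40 mg weekly.** Both readings agree with Section 5.1: 80 mg per two weeks becomes 40 mg, and re-escalation restores 80 mg.

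**The case against.** The best defence is that the entry is a strength. Table 4 and Section 5.5.2.1 use the same figure for the vial. Where Appendix G does mean a fixed 40 mg, at the third flare, it marks the step as not weight-based and prints the dose and the volume on lines of their own. The de-escalation and re-escalation rows have neither line. This stands as a possible reading. A reader might infer that the protocol raises the dose in small children, and the documents do not support so flat a statement. The defence leaves a gap, though, because on that reading Appendix G states no dose for these children.

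A second defence is procedural. The Medical Monitor is to approve each de-escalation and re-escalation beforehand, and site staff weigh the child and state the volume at every visit. This is a partial safeguard, but it supplies no written dose to approve against.

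Third, the affected group is narrow: Week 8 responders who flare twice, then hold remission for eight weeks on the weight-based step; the two-week amount rises only under 33.3 kg. The 2.38-fold figure is at the lowest tabulated weight. This stands.

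Fourth, a reader might infer that exposure, adverse event attribution and the dose-change blood samples are distorted. SAP Section 9.1 measures exposure in days. SAP Section 11.2 groups post-flare events by re-induction or not. The de-escalation sample is drawn before the change. None of these depends on the mg amount given afterwards.

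**Conclusion.** The inconsistency is real and should be corrected, within limits. For a subject on open-label 0.6 mg/kg weekly, Section 5.1 and Appendix G do not together say what de-escalation and re-escalation consist of. Read as a dose, Appendix G conflicts with the body text, by up to 2.38-fold on the two-week amount at 14 kg and with no increase above 33.3 kg. Read as a strength, it leaves the dose unstated. The documents do not settle which reading is meant. Figures 3 and 4, the dose-escalation schematics, could not be seen and might narrow the question.

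Confirmatory efficacy is unaffected, because SAP Section 6.0 already counts subjects as non-responders from their first re-randomization for flare. The consequence is confined to dosing safety in a few small children and to PK samples taken after the change. That the number is small is a judgement from the sequence of events required; the documents give no count.

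**What to change.** Reconcile Section 5.1, and the matching text in the Synopsis and Section 5.5.1, with both Appendix G tables. For each open-label step (0.6 mg/kg weekly and fixed 40 mg weekly), state who may de-escalate and what de-escalation and re-escalation consist of. In the table, print product strength separately from dose and volume, as the third-flare row does. If the intention is that only one step may de-escalate, the eligibility sentence needs to say so. The sponsor's clinical team must decide what is intended; no dose is proposed here.

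The cost is a protocol clarification and a letter to sites. No visits, procedures or analyses are added.
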